10.5 Planned Methods of Analysis

10.5.1 General Considerations

The primary objective of this study is to evaluate the effect of AMG 334 compared to placebo on the change from baseline in mean monthly migraine days, in subjects with episodic migraine.

Summary descriptive statistics by each treatment group will be tabulated at each visit. For continuous endpoints, the descriptive statistics include: number of observations, means, medians, standard deviations, standard errors, first and third quartiles, minimums and maximums, and two-sided 95% confidence intervals of the means (except for safety laboratory analyses). For categorical endpoints, the summaries will contain the number and percentage of subjects falling into each category. The number of days on investigational product and the total dose of investigational product will be summarized using descriptive statistics.

For all efficacy endpoints, nominal p-values will be provided for the comparisons between each AMG 334 treatment group vs the placebo group without adjusting for multiple comparisons.

In addition, the dose-response data will be depicted graphically to support a bridging strategy.

The full analysis set (FAS) will be utilized to tabulate demographic data, baseline disease characteristics and subject disposition. The efficacy analysis set will be utilized to analyze efficacy endpoints. The per-protocol analysis set will be used for the sensitivity analyses of primary and secondary endpoints. The safety analysis set will be used to analyze safety endpoints during the double-blind phase. The OLAS will be used to analyze the data collected during the **OLTP**.

Details of all statistical methods will be provided in the Statistical Analysis Plan.

The proportion of subjects who administer a full dose of AMG 334 in home-use will be summarized by treatment group at CHU day 29 and day 57. For all subjects who have not discontinued IP, a subject report of full dose administration will be

considered a “yes” response, and a subject report of partial or no dose administered will be considered a “no” response. The proportion of each possible pattern of responses across the 2 visits will also be estimated. Ninety-five percent confidence intervals will be provided for each group and the difference in proportions between the groups. Subject incidence of adverse events, serious adverse events, and adverse device effects will be summarized by system organ class and preferred term for subjects enrolled in the CHU substudies. Details of the analysis of the CHU substudy will be described in a separate Statistical Analysis Plan.

10.5.2 Primary Efficacy Endpoint

The primary endpoint, the change from baseline in mean monthly migraine days over the last 3 months (months 4, 5, and 6) of the double-blind treatment phase, will be analyzed using the repeated measures linear mixed effects model including treatment group, baseline value, stratification factor, scheduled visit, and the interaction of treatment group with scheduled visit, without any imputation for missing data. The primary endpoint will be tested for each AMG 334 treatment group compared to the placebo group sequentially at a 2-sided significance level of 0.05 in the order of AMG 334 140 mg vs. placebo, 70 mg vs. placebo and 28 mg vs. placebo. The lower dose group will be tested only when the higher dose group is considered statistically significant. The mean change from baseline for each treatment group, and the treatment difference, 95% confidence interval will be reported.

Sensitivity analyses for the primary endpoint include: (1) the same analysis using the per-protocol analysis set, (2) the last observation carried forward (LOCF) to handle missing data **with analysis of covariance (ANCOVA) model**, and (3) **multiple imputation (MI) with assumptions of missing at random (MAR) and missing not at random (MNAR) to handle missing data.**

Once the superiority of AMG 334 70 mg and 140 mg compared to placebo is established, a dose-response model will be assessed using the MCP-Mod approach including all treatment groups. Using linear, log linear, E_{max} and sigmoid E_{max} model as candidate models, a dose response will be tested with type 1 error rate of 0.05 and identify the dose-response model that would establish the dose response relationship with best fit. The minimal effective dose identified and treatment effect at each treatment group will be estimated from the model.

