Subjects assigned to receive AMG 334 140 mg QM SC during the open-label phase will not have the option to decrease open-label AMG 334 from 140 mg QM to 70 mg QM. A safety follow-up visit occurs 16 weeks after the last dose of investigational product. Subjects will use an electronic diary (eDiary) every day throughout the baseline phase and double-blind treatment phase and for the first 6 months and **between the week 72 and week 76 study visits and between the week 96 and week 100/early termination (ET) study visits** of the OLTP to report information about their migraine and non-migraine headaches and acute headache medication use. Subjects will have in-clinic study visits monthly after the week 4 visit.

For a full list of study procedures, including the timing of each procedure, please refer to [Section 7](#) and the Schedule of Assessments ([Table 2-Table 3](#), and [Table 4](#) for CHU substudy).

Statistical Considerations: The primary analysis will occur after all subjects have completed their week 24 visit (or discontinued from the study). The final analysis for the study will occur after all subjects have completed safety follow-up through week 112 or discontinued from the study. Using the treatment effect compared to placebo of -1.12 and -1.30 for the AMG 334 70 mg and 140 mg dose groups, respectively and a common standard deviation of 2.8 based on a Japan topiramate trial (www.clinicaltrials.gov), the planned sample size of 131 subjects in the placebo, 70 mg and 140 mg dose groups will provide 90% and 96% power for a two-sided test with significance level of 0.05 to show the superiority of AMG 334 70 mg and 140 mg compared to placebo, respectively. The proposed number of subjects in the 28 mg (n=66) dose group with the placebo (n=131), the 70 mg (n=131) and the 140 mg (n=131) dose groups is sufficient to demonstrate a dose-response using the Multiple Comparison Procedure–Modelling (MCP-Mod) analysis with the minimum power of 95% and provide the estimates of response in a Japanese population, using an assumed treatment effect of -0.55 for the AMG 334 28 mg dose group.

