For the primary endpoint of change in monthly migraine days from baseline to the last 4 weeks of the 12-week double-blind treatment phase, only the 70 mg dose was significantly different from placebo (-3.40 days vs. -2.28 days, $p=0.021$). The 7 mg and 21 mg doses only demonstrated changes of -2.18 days and -2.39 days, respectively, which were not significantly different from placebo (Figure 1). The results of the primary endpoint were consistent with those of the secondary endpoints. The 70-mg dose produced statistically significant improvements in multiple secondary and exploratory outcome measures, including the 50% responder rate, monthly headache days, and monthly migraine-specific medication treatment days, while neither the 7-mg nor the 21-mg dose resulted in improvements in these measures. Exposure-response analyses over a large range of PK exposures indicate that 70 mg is the lowest dose that results in efficacious concentrations, and suggested that greater reductions in migraine day could be achieved with higher exposures. Therefore, to more fully establish the dose-response relationship, a higher dose, 140 mg, also is included in the present study.

A lower dose also was selected in order to maximize the probability of having at least 2 doses in the current study that demonstrate some efficacy, and that there is differential efficacy achieved with at least 2 doses. The 28-mg QM dose was chosen as it is expected to result in numerical improvements in the monthly migraine days, but not to achieve full efficacy. Using a pharmacokinetic-pharmacodynamic (PK-PD) model developed for the AMG 334 exposure and migraine day data from the study 20120178, the treatment effect in Japanese patients was predicted for the 28-mg QM dose. According to the model predictions, the expected mean (SE) placebo-corrected change from baseline in monthly migraine days with the 28-mg dose will be -0.55 (0.68) days in Japanese patients. The intermediate dose of 70 mg QM, which was shown to be efficacious in study 20120178, is predicted to result in a mean (SE) placebo-corrected change from baseline in monthly migraine days of -1.51(0.36) days in Japanese patients.

Figure 1. Change From Baseline on Mean Monthly Migraine Days by Treatment Groups in the Double-Blind Treatment Phase of Study 20120178

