AMG 334 140 mg has been evaluated for the prevention of episodic migraine in a global Phase 3 study (20120296) with a 24-week double-blind treatment phase. The study randomized 955 subjects (AMG 334 70 mg [n = 317], AMG 334 140 mg [n = 319], and placebo [n = 319], QM SC) with a history of migraine with or without aura for ≥ 12 months and a monthly migraine frequency of ≥ 4 to < 15 migraine days. For the primary endpoint of change in monthly migraine days from baseline to the last 3 months (months 4, 5, and 6) of the 24-week double-blind treatment phase, the 70 mg and 140 mg doses were significantly different from placebo (-3.23 days and -3.67 days vs. -1.83 days, $p < 0.001$). Both doses produced statistically significant improvements in the secondary outcome measures of 50% responder rate and monthly migraine-specific medication treatment days. The results of the other secondary endpoints were consistent with those of the primary endpoint. Across the primary and all secondary endpoints, AMG 334 140 mg showed numerically greater efficacy than 70 mg. At the end of the double-blind treatment phase, subjects in each treatment group are re-randomized 1:1 in a blinded fashion to AMG 334 70 mg or AMG 334 140 mg for the 28-week active treatment phase, which is ongoing.

During the placebo-controlled double-blind treatment phase of the 20120296 study, treatment-emergent adverse events were reported in 57.3%, 55.5%, and 63.0% of subjects in the AMG 334 70 mg, AMG 334 140 mg, and placebo groups, respectively, and most were Common Terminology Criteria for Adverse Events (CTCAE) grade 1 or 2 (mild to moderate in severity). Study drug discontinuations due to adverse events were reported in 7 subjects (2.2%), 6 subjects (1.9%), and 7 subjects (2.2%) in the AMG 334 70 mg, AMG 334 140 mg, and placebo groups, respectively. The most frequent adverse events occurring in $\geq 2\%$ of all AMG 334 treated subjects were nasopharyngitis, upper respiratory tract infection, sinusitis, constipation, arthralgia, fatigue, and nausea. Serious adverse events were reported in 2.5%, 1.9%, and 2.2% of subjects in the AMG 334 70 mg, AMG 334 140 mg, and placebo groups, respectively. No serious adverse event occurred in more than 1 subject, except cholelithiasis which was reported by 2 subjects in the AMG 334 70 mg group (one of whom had clear risk factors). Study 20120296 and Study 20120309 are being monitored by the same independent Data Monitoring Committee (DMC).

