10.2 Sample Size Considerations

The primary endpoint is the change from baseline in mean monthly migraine days over the last three months (months 4, 5, and 6) of the double-blind treatment phase. Using the treatment effect compared to placebo of -1.12 and -1.30 for the AMG 334 70 mg and 140 mg dose groups, respectively and a common standard deviation of 2.8 based on a Japan topiramate trial (www.clinicaltrials.gov), the planned sample size of 131 subjects in the placebo, 70 mg and 140 mg dose groups will provide 90% and 96% power for a two-sided test with significance level of 0.05 to show the superiority of AMG 334 70 mg and 140 mg compared to placebo, respectively. The proposed number of subjects in the 28 mg (n=66) dose group with the placebo (n=131), the 70 mg (n=131) and the 140 mg (n=131) dose groups is sufficient to demonstrate a dose-response using MCP-Mod analysis with the minimum power of 95% and provide the estimates of response in a Japanese population, using an assumed treatment effect of -0.55 for the AMG 334 28 mg dose group.

Clinical Home Use Substudy

Approximately 50 subjects will be enrolled in to the CHU substudy. The following assumptions are made based on the minimum sample size of 50 subjects: 5% of subjects per treatment group discontinue IP and 90% of the remaining subjects respond that they administered a full dose. As such, the anticipated distribution of responses per treatment group at a planned visit would be 5% categorized as not attempting due to discontinuing IP, 85.5% responding that they administered a full dose, and 9.5% responding that they did not administer a full dose. The associated 95% confidence interval halfwidths with 25 subjects per group are

8.5%, 13.8%, and 11.5%, respectively. The anticipated 95% confidence interval half width for the difference between treatment groups in the proportion of subjects administering a full dose is 19.5%. The discontinuation rate is expected to be less than 5% and the rate of administering a full dose is expected to be greater than 90%, and therefore these calculations are anticipated to be lower bounds. Calculations were performed using nQuery Advisor 7.0.

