3.2 Sample Size

The primary endpoint is the change from baseline in mean monthly migraine days over the last three months (months 4, 5, and 6) of the DBTP. Using the treatment effect compared to placebo of -1.12 and -1.30 for the AMG 334 70 mg and 140 mg dose groups, respectively and a common standard deviation of 2.8 based on a placebo-controlled dose-finding study of JNS019 (topiramate) in migraine patients (www.clinicaltrials.gov), the planned sample size of 131 subjects in the placebo, 70 mg and 140 mg dose groups will provide 90% and 96% power for a two-sided test with significance level of 0.05 to show the difference of AMG 334 70 mg and 140 mg compared to placebo, respectively. The proposed number of subjects in the 28 mg (n=66) dose group with the placebo (n=131), the 70 mg (n=131) and the 140 mg (n=131) dose groups is sufficient to demonstrate a dose-response using Multiple Comparison Procedure – Modelling (MCP-Mod) analysis with minimum power of 95% and provide estimates of response in a Japanese population, using an assumed treatment effect of -0.55 for the AMG 334 28 mg dose group.

Power calculations are derived through nQuery 7.0.

4. Study Endpoints and Covariates

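### The stated 95% minimum power for the MCP-Mod dose-response test ignores the plan's own precondition; on the planning means the procedure as planned has about 88%

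*Protocol*

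**What the plan says.** Protocol 10.2 assumes effects against placebo of -0.55, -1.12 and -1.30 days for 28, 70 and 140 mg, a common SD of 2.8, and 131, 66, 131 and 131 subjects on placebo, 28, 70 and 140 mg. It says that the 70 mg and 140 mg comparisons "will provide 90% and 96% power for a two-sided test with significance level of 0.05". The next sentence says that the sample "is sufficient to demonstrate a dose-response using MCP-Mod analysis with the minimum power of 95" percent. The synopsis makes the same statement, and SAP 3.2 says "is sufficient to demonstrate a dose-response using Multiple Comparison Procedure – Modelling (MCP-Mod) analysis with minimum power of 95" percent. None of the three mentions a condition.

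Protocol 10.5.2 tests the doses against placebo in the order 140, 70, 28 mg, each at two-sided 0.05 and each lower dose only if the higher one is significant. It then says: "Once the superiority of AMG 334 70 mg and 140 mg compared to placebo is established, a dose-response model will be assessed". The candidate models are linear, log-linear, Emax and sigmoid Emax, tested at a type I error of 0.05. The documents give no shape parameters for the candidates and do not say whether that 0.05 is one-sided or two-sided.

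Apart from its abbreviation list, the SAP names MCP-Mod only in Section 3.2. SAP Section 11 lists no changes from the protocol-specified analyses, so the precondition stands.

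**The concern.** The two sections describe different procedures. The power statement describes MCP-Mod performed in every trial. The analysis section describes MCP-Mod performed only after two pairwise successes, one of which has a planned power of 90%. A reader of 10.2 takes 95% as the chance that the planned dose-response analysis succeeds, and for the procedure in 10.5.2 that figure cannot be right.

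This matters because dose-response is one of the trial's purposes. Protocol 2.3 gives establishing the dose-response relationship in Japanese subjects as a reason for the choice of doses. Protocol 10.4.3 seeks an optimal dose. The minimal effective dose in 10.5.2 is to be estimated from the model that sits behind the precondition.

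**Working it through.** **Inputs (Protocol 10.2 and 10.5.2).** Effects 0.55, 1.12 and 1.30 days (as reductions) for 28, 70 and 140 mg; SD 2.8; n = 131, 66, 131, 131; pairwise tests at two-sided 0.05.

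**Step 1: reproduce the pairwise power.** Standard error of a difference between two arms of 131:

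SE = 2.8 × √(2/131) = 0.346.

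Power ≈ Φ(effect/SE − 1.96):

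- 70 mg: 1.12/0.346 = 3.237; Φ(1.277) = 0.899 (0.897 with the noncentral t). Stated 90%.
- 140 mg: 1.30/0.346 = 3.758; Φ(1.798) = 0.964 (0.963 with the noncentral t). Stated 96%.

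Both reproduce.

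**Step 2: check the 95% for MCP-Mod on its own.** I simulated the maximum optimal-contrast t-test over the four named models on the planning means. The shape parameters had to be assumed, so five sets were tried, at both one-sided levels:

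| One-sided level | Power, planning means (five sets) | Lowest power when the true curve is a candidate shape with maximum effect 1.30 |
|---|---|---|
| 0.05 | 98.9% to 99.2% | 98.3% |
| 0.025 | 97.5% to 98.2% | 96.4% |

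A minimum of 95% therefore holds for MCP-Mod without the precondition.

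**Step 3: add the precondition.** The upper bound follows from the plan's own figures:

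P(140 and 70 both significant, and MCP-Mod significant) ≤ P(70 significant) = 90%.

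For the value itself, the two comparisons share the placebo arm and all three arms are equal in size, so their test statistics have correlation 0.5:

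P(Z₁ < 1.277, Z₂ < 1.798; ρ = 0.5) = 0.878.

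Simulating the whole procedure gives 87.7% for all five candidate sets at both levels. MCP-Mod was significant in at least 99.99% of the trials that passed the precondition, so the unstated shape parameters and sidedness hardly matter here.

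**Step 4: dependence on the true effects** (SD and n unchanged; probability that both doses beat placebo).

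| 70 mg | 140 mg | Basis | Probability |
|---|---|---|---|
| -1.12 | -1.30 | Planning means, Protocol 10.2 | 87.8% |
| -1.40 | -1.84 | Phase 3 study: -3.23 and -3.67 minus -1.83, Protocol 2.3 | 98.1% |
| -1.51 | -1.30 | Model prediction at 70 mg (Protocol 2.3), planning value at 140 mg | 95.8% |
| -1.12 | -2.24 | Assumed straight line through -1.12 at 70 mg | 89.9% |
| -0.65 | -1.30 | Assumed straight line through -1.30 at 140 mg | 46.4% |

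The two straight-line rows are illustrations only. The last has a 70 mg effect well below the planned one. With 140 mg held at -1.30, the 70 mg effect would have to be about -1.40 for the probability to reach 95%.

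**The case against.** The best reply is that nothing has been miscalculated. The 95% is attached to the MCP-Mod analysis, where it is correct. The whole paragraph reports power test by test, and even the 90% for 70 mg ignores that 70 mg is tested only after 140 mg. The precondition is stated openly in 10.5.2, so a reader of both sections can see the ceiling. This explains how the gap arose but does not close it: no passage makes the 95% conditional, and all three statements speak of demonstrating a dose-response.

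A second reply is that 88% belongs to one set of inputs. That is fair. The Phase 3 result, "significantly different from placebo (-3.23 days and -3.67 days vs. -1.83 days", gives 98%. The model prediction at 70 mg, a placebo-corrected change in "monthly migraine days of -1.51(0.36) days in Japanese patients", gives 96%. The mixed model adjusts for baseline and stratum, and if that cut the residual SD from 2.8 to about 2.46 the planning means would give 95%; dropout would work the other way. The documents quantify neither. The 95% was justified on the planning means and SD 2.8, and on those it does not hold for the planned procedure.

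Third, the practical harm is limited, and that stands. Dose-response is listed as an exploratory objective. A significant 140 mg result already contradicts a flat curve. Protocol 10.5.1 also says, without any precondition, that "the dose-response data will be depicted graphically to support a bridging strategy". The SAP leaves the bridging analysis to a supplement that was not available, so more may be said there.

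**Conclusion.** The concern holds. On the plan's own inputs, the procedure in Protocol 10.5.2 demonstrates a dose-response with probability of about 88%, and never above the 90% power of the 70 mg comparison, against a stated minimum of 95%. The chance of failure is about 12%, more than double what the statement implies. This rests on the planning effects, SD 2.8, full group sizes, and reading the sentence in 10.5.2 as a precondition, which is its natural sense given the sequential tests described just before it. It does not depend materially on the assumed candidate shapes. The error lies in the power statement: the primary comparisons, their error control and the sample size are sound. It should be corrected.

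**What to change.** In the synopsis, Protocol 10.2 and SAP 3.2, add after the MCP-Mod power statement: *The minimum of 95% is the power of MCP-Mod run without a precondition. Under Section 10.5.2 MCP-Mod follows significant results for 140 mg and 70 mg; on the planning means the power of this procedure is about 88%.* The sponsor could add that the power for 70 mg within the 140-70-28 sequence is also about 88%, by the same calculation. Giving the assumed candidate shapes and the sidedness of the MCP-Mod test would let a reader check the 95%. The cost is one sentence in each of three places and a lower published figure, with no additional subjects.

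Alternatively, the sponsor may delete the precondition from Protocol 10.5.2 and run MCP-Mod in every case at its own 0.05, labelled as outside the family-wise control of the pairwise tests. The 95% then stands and only that sentence changes, because the SAP does not repeat the precondition. The price is a dose-response claim without that error control. This is a design choice and is not needed to correct the power statement.

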10.5.3 Secondary Efficacy Endpoints

- Achievement of at least a 50% reduction from baseline in mean monthly migraine days over the last three months (months 4, 5, and 6) of the double-blind treatment phase

The 50% responder endpoint will be analyzed using a stratified CMH test after the missing data are imputed as non-response. The odds ratio for each AMG 334 treatment group vs placebo group and associated 95% confidence intervals will be reported.

Sensitivity analyses for **the binary endpoint** include: (1) **CMH test** using the per-protocol analysis set, and (2) **generalized linear mixed model without imputation of missing data, and (3) logistic regression model for each visit after the missing data are imputed as non-responders.**

- Change from baseline in mean monthly acute migraine-specific medication treatment days over the last three months (months 4, 5, and 6) of the double-blind treatment phase

The same analysis methods will be used as for the primary endpoint ([Section 10.5.2](#)).

